#### **10.17. Replacement of Patients**

Patients withdrawn from the study will not be replaced.

#### **10.18. Unscheduled Visits**

Unscheduled visits may be performed if required for assessments of laboratory parameters or clinical safety.

#### **10.19. Laboratory Procedures**

All clinical safety laboratory determinations will be performed by Quintiles Central Laboratory Services. The study staff will send the samples to the appropriate address (provided in the Central Laboratory Manual) by shipping them in the laboratory kits supplied by Quintiles Central Laboratory. Central laboratory reports will be sent to the Investigator for evaluation.

An Investigator may choose to use a local laboratory to evaluate a potential adverse event. However, for the purpose of this study, data from local laboratories will not be recorded or used in the analysis of safety. The Sponsor will not cover costs associated with the use of a local laboratory.

#### **10.20. Early Termination / Withdrawal Visits**

The Principal Investigator may discontinue a patient from the study for any of the following reasons: the patient no longer meets eligibility criteria, it is in the patient's best interest, patient preference, concurrent illness, noncompliance, etc. Patients will be informed prior to study entry that they are free to withdraw from the study at any time and for any reason. If a patient is discontinued from the study, the Investigator will immediately notify the Sponsor or the site CRA of the withdrawal.

Patients who withdraw from the study prior to completion for any reason (adverse event, withdrew consent, etc.) will have their study medication tapered over a 3-week period, reducing their daily dose by one-third per week and then return for a final visit. Patients who discontinue early during the first year of the open-label extension study will complete all assessments and evaluations scheduled for Study Visit 5. Patients who discontinue early during the second year of the open-label extension study will complete all assessments and evaluations scheduled for Study Visit 8. Patients who discontinue early during the third year of the open-label extension study will complete all assessments and evaluations scheduled for Study Visit 11 and complete all assessments and evaluations scheduled for Visit 14 if patient discontinued early during the fourth year of the open-label extension study (Refer to Study Flow Chart in Appendix A).

**10.20.1. Reasons for Withdrawal**

Patients are free to discontinue their participation in the study at any time and without prejudice to further treatment at their local site. The Investigator must withdraw any patient from the study if that patient requests to be withdrawn.

Patients withdrawn from the study will not be replaced, regardless of the reason for withdrawal. The patient's participation in this study may be discontinued due to the following reasons:

- Patient experiences an intolerable AE.
- Investigator decides patient has an "unsatisfactory response – efficacy."
- Patient becomes pregnant.
- Patient is unwilling or unable to continue the study.
- Patient is non-compliant with study procedures.
- Patient needs medication not allowed in the protocol.
- Any clinically significant change in patient's medical condition.
- Persistent ALT or aspartate aminotransferase (AST) above 3 times the ULN; will be confirmed by repeating laboratory assessment within 1 week.
- ALT or AST levels are above 5 times the ULN at any time during the study.
- Confirmed QTc prolongation defined as QTc (Bazett's) >500 msec or an increase in QTc (Bazett's) of >60 msec from baseline.
- Investigator decides that withdrawal from the study is in the best interest of the patient.
- Request of the Sponsor
- Hematological reasons or infections – for all such patients, the investigator shall report these in an expedited manner, whether or not they are considered serious or unexpected.

**10.20.2. Handling of Withdrawals**

If a patient is withdrawn from the study either at the patient's request or at the Investigator's decision or the patient fails to return, every effort should be made to determine the reason. This information will be recorded on the patient's case report form (CRF) and recorded by IVRS.

All patients who withdraw from the study prematurely, regardless of cause, should have their study medication tapered over a 3-week period, reducing their daily dose by one-

third per week, and follow the tapering procedures outlined in Section 9.12 (Tapering Period).

It is important to obtain follow up data for any patient withdrawn because of an AE, abnormal laboratory test, or ECG finding. In any case, every effort must be made to undertake safety follow up procedures.

## **11. STATISTICAL MEASUREMENTS, EVALUATIONS AND ANALYTICAL METHODS**

### **11.1. Assessment of Efficacy**

Monthly total seizure rates will be calculated for the entire open-label part of Study VRX-RET-E22-304 and described statistically. Monthly total seizure rates observed during the open-label extension period will be compared to the monthly total seizure rates observed during the Baseline phase of the double-blind study VRX-RET-E22-302. The percent change in monthly total seizure rates from the Baseline phase will be classified into <0, [0, 25), [25, 50), [50, 75), [75, 100] and described. The responder rate during the open-label study (defined as a reduction in seizure frequency  $\geq 50\%$ ) will also be summarized using descriptive statistics.

The number of seizure free days, in percent to the individual duration of the open-label treatment, will be calculated and summarized using descriptive statistics. This percentage will be classified into [0, 25), [25, 50), [50, 75), [75, 95), [95, 100), [=100] and described statistically.

All-cause withdrawal rates will be calculated as a percentage and respective "times to event" will be described by a Kaplan-Meier survival curve. Specific reasons for withdrawal will also be described separately.

This is an open-label extension study with the emphasis on safety. Efficacy is not the primary objective of this study unlike the double-blind study VRX-RET-E22-302. Descriptive statistics of efficacy measures such as number of patients, mean, standard deviation, median, minimum and maximum will be provided for continuous variables. The number and percentages in each category will be presented for categorical data. The pairwise t-test will be used to assess whether the retigabine treatment remains effective in the open-label extension study if necessary. The pairwise t-test may be sorted by the geographic region [Central/Eastern Europe vs. Rest of World (ROW)]. The safety assessments will use essentially the same descriptive statistics and pairwise t-test as mentioned above for efficacy. The complete details of efficacy analyses will be described in the Statistical Analysis Plan.

## 11.2. Assessment of Safety

Adverse events (AEs) will be monitored from the start of this extension study (informed consent provided by patient at the Baseline visit) until 30 days after administration of the last dose of study drug (end of study drug taper-off). Treatment-emergent adverse events (TEAEs) will be summarized with respect to overall incidence, as well as severity and relationship of the AEs to the study drugs. AEs that result in dose modification, discontinuation of the study drug, or serious adverse events will also be summarized

AEs with onset after the initiation of study drug and within 30 days after the last dose of study drug may be considered treatment-emergent. This will include any AE with onset prior to initiation of study drug that increased in severity during the treatment period. All reported AEs including those with onset more than 30 days after the last dose of study drug will be included in the data listings.

Abnormal changes in laboratory parameters that are not disease-related will be monitored and recorded throughout the study.

All adverse events will be encoded according to MedDRA 8.0. Treatment emergent adverse events (TEAE) will be analyzed, i.e. all adverse events starting or worsening between start of long-term extension study up to 30 days after end of study drug taper-off. Incidences on preferred term and body system basis will be calculated for all TEAEs.

Different categories for causality will be recorded in the CRFs, and these 4 categories (DEFINITE, PROBABLE, POSSIBLE, and NOT RELATED) are defined in Section 11.3 (Criteria for Determining Relationship to Study Drug) of this protocol.

In addition, all SAEs and all AEs leading to premature discontinuation will be presented as separate listings. TEAE from both studies (double-blind and open-label extension) will be combined, i.e. each patient will be counted just once (with patient's respective TEAE).

Other safety evaluations, such as vital signs, physical and neurological examinations, laboratory variables, ECG variables, post-void residual bladder ultrasound, and AUA symptom index will be analyzed descriptively.

Besides descriptive statistics of the safety evaluations will be presented, the incidence of TEAEs will be compared across treatment group using Fisher's Exact test, only for those events with an incidence of  $\geq 5\%$  over all treatment groups. Fisher's Exact test will be applied if necessary for other safety evaluations (vital signs, physical and neurological examinations, laboratory variables, etc.). QTc interval prolongations will be examined by using both Bazett's and Fridericia's QT correction formulas. The complete details of safety analyses will be described in the Statistical Analysis Plan.

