## **9. STUDY DESIGN**

This is an open-label extension study of the placebo controlled, double-blind Study VRX-RET-E22-302. Patients will be treated with 600-1200 mg/day of retigabine as an adjunct therapy to their current antiepileptic medications (AEDs) or vagal nerve stimulation as established in Study VRX-RET-E22-302. Following completion of the Transition Phase of the double-blind study (Study VRX-RET-E22-302), treatment in this open-label extension study will be continued until retigabine is approved and commercially available, or until the program is discontinued, followed by a 3-week tapering period and a 30 day post-study period for collection of adverse events.

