#### **10.16. Tapering Period**

All patients who discontinue early from study treatment during the open-label extension study will have their study medication tapered over a 3-week period, reducing their daily dose by one-third per week, and return immediately for a final visit. The patients will be instructed to take the tablets from their existing study medication bottles and to follow this tapering procedure:

- During the first week of tapering, patients will no longer take the afternoon dose.
- During the second week of tapering, patients will no longer take the morning and the afternoon doses.
- During the third week of tapering, patients will take no study medication (but will continue their existing background AEDs).

During the first year, these patients should then return for a final visit to complete all assessments and evaluations scheduled for Study Visit 5. During the second year, these patients should then return for a final visit to complete all assessments and evaluations scheduled for Study Visit 8. During the third year, these patients should then return for a final visit to complete all assessments and evaluations scheduled for Study Visit 11. During the fourth year, these patients should then return for a final visit to complete all assessments and evaluations scheduled for Study Visit 14 (Refer to Study Flow Chart in Appendix A).

During the tapering period, a new background AED should not be added until after the patient's final visit unless clinically necessary for patient safety. Unused current study medication bottles will be collected to ascertain compliance. Current study seizure

diaries will be collected and reviewed. Concomitant medications and AED usage will be documented, and adverse events will be recorded.

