##### 12.4.1. Adverse Events Follow-Up

AEs will be recorded from the start of this extension study (informed consent provided by patient at the Baseline visit) until 30 days after administration of the last dose of study medication (end of study medication taper-off). All post-treatment events will be collected through spontaneous reporting by the patient. All AEs and SAEs will be followed until the event resolves, the condition stabilizes, the event is otherwise explained, or the patient is lost to follow up. The Investigator is responsible for ensuring that follow up includes any supplemental investigations as may be indicated to elucidate the nature and/or causality of the AE. This may include additional laboratory tests or investigations, histopathological examinations, or consultation with other health care professionals, as is practical.

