Probable	Temporal association, other etiologies are possible but unlikely. The event may respond if the study drug is discontinued.
Definite	Established temporal association with administration of the study drug with no other probable cause. The event should resolve when the study drug is discontinued and recur on re-challenge.

The intensity and relationship assessments to study drug are recorded on the AE CRF page.

Treatment-emergent AEs (TEAEs) will be tabulated, i.e., those events which are not present at baseline or worsened in severity following the start of treatment. Any adverse events starting more than 30 days after the last administration of study drug will not be tabulated.

The onset date of an adverse event will be compared to the date of first dose of study medication in this extension study to determine if the adverse event is treatment emergent

or not. Adverse events with an onset date on or after the date of first dose of study medication will be classified as treatment emergent.

The following adverse event summaries will be provided:

- A summary of the number and percentage of patients reporting a treatment emergent adverse event by body system, and preferred term
- A summary of the number and percentage of patients reporting a treatment emergent adverse event by maximum intensity, body system and preferred term
- A summary of the number and percentage of patients reporting a treatment emergent adverse event by relationship to study drug, body system and preferred term
- A summary of the number and percentage of patients reporting a treatment emergent adverse event leading to dose modification by body system and preferred term

For each patient and each adverse event, the worst severity recorded will be attributed and used in the by-severity summaries. Similarly, the worst causality (most related to treatment) will be attributed and used in the by-causality summaries. If severity or causality are missing, the worst case will be assumed.

The date the AE started should be well collected in CRF data. However, in the unlikely case that the AE start date is missing, the AE date will imputed be as follows.

Scenarios			Imputed AE Onset Date
Day	Month	Year	
missing			
If the month and year of the AE are the same as the month and year of the first dose date in the extension, use the day of the first dose date.
 
Otherwise use 1 for day.

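### The adverse-event window equates the last dose with the end of taper-off, but taper week 3 is drug-free, so onsets about 31 to 37 days after the last dose are treatment-emergent under the protocol's analysis definition yet outside the SAP incidence tables

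*Protocol*

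**What the plan says.** **Collection.** Protocol 11.2 (first paragraph) monitors adverse events "until 30 days after administration of the last dose of study drug (end of study drug taper-off". Protocol 12.4.1, the Appendix A footnote on early discontinuation and the opening of SAP 4.5.2 carry the same equation. The study design (Protocol 9 and 9.4, synopsis, SAP 3.1) describes the end of treatment as "followed by a 3-week tapering period and a 30 day post-study period for collection of adverse events".

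**Treatment-emergent definition.** Protocol 11.2 gives two. In the second paragraph, events with onset "within 30 days after the last dose of study drug may be considered treatment-emergent". In the fourth paragraph, the events to be analysed are "all adverse events starting or worsening between start of long-term extension study up to 30 days after end of study drug taper-off"; the synopsis agrees with this one.

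**Tabulation.** SAP 4.5.2: "Any adverse events starting more than 30 days after the last administration of study drug will not be tabulated". A separate sentence there classifies any onset on or after the first extension dose as treatment-emergent and sets no upper limit.

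**Taper.** Protocol 10.16 drops the afternoon dose in week 1 and the morning dose as well in week 2. Then: "During the third week of tapering, patients will take no study medication (but will continue their existing background AEDs". Under 9.7.5 and 10.16 the final visit follows immediately after the taper. After treatment, Protocol 12.4.1 states: "All post-treatment events will be collected through spontaneous reporting by the patient".

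**The concern.** The bracket asserts that two dates coincide, and the protocol's own taper schedule separates them by a week. Everything that depends on the date then has two possible answers: how long a site records events, which events are treatment-emergent, and which enter the incidence tables.

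Safety and tolerability are the primary objective, and treatment-emergent incidence is one of its main summaries. Its numerator should not depend on which sentence the programmer or the site happens to follow. The tabulation part can be settled at any time before the analysis. The collection part cannot, because an event that a site did not record on day 34 cannot be recovered by later correcting the SAP.

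**Working it through.** The plan states no figure to reproduce; the check is calendar arithmetic.

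**Inputs (Protocol 10.16, three daily doses, early discontinuation)**

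- Taper length: 3 weeks = 21 days.
- Fraction of the daily dose taken: week 1 = 2/3, week 2 = 1/3, week 3 = 0.
- Post-treatment window: 30 days (Protocol 11.2, SAP 4.5.2).

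**Steps**

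1. Last dose: end of week 2, taper day 14.
2. End of taper: taper day 21.
3. Gap: 21 − 14 = 7 days.
4. Window anchored on the last dose closes on day 30 after the last dose.
5. Window anchored on the end of taper closes on day 7 + 30 = 37 after the last dose.
6. Disputed onsets: days 31 to 37, that is 37 − 30 = 7 days.

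**The passages side by side**

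| Place | Anchor | Closes, days after last dose |
|---|---|---|
| Protocol 11.2 first paragraph, 12.4.1, Appendix A footnote; SAP 4.5.2 opening | last dose and end of taper, equated | 30 or 37 |
| Protocol 11.2 second paragraph | last dose | 30 |
| SAP 4.5.2 tabulation cut-off | last administration | 30 |
| Protocol 11.2 fourth paragraph, synopsis | end of taper-off | 37 |
| Protocol 9 and 9.4, synopsis design, SAP 3.1 | after the 3-week taper | 37 |

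**Worked case.** An onset on day 34 after the last dose is day 34 − 7 = 27 after the end of taper. It is treatment-emergent under the fourth paragraph of 11.2, falls outside the second paragraph, and is not tabulated under SAP 4.5.2.

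**Is it a version effect?** No. The SAP was written to Amendment 1, but the relevant wording of 10.16, 11.2 and 12.4.1 is the same in Amendments 1 and 2.

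**Side calculation on ascertainment.** With the final visit about 7 days after the last dose, the time left without scheduled contact is 30 − 7 = 23 of 30 days (77%), or 37 − 7 = 30 of 37 days (81%).

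**The case against.** The best defence is that the bracket is a definition: for this protocol, last dose means end of taper-off, and then every passage gives one window. That would reconcile the text if it were stated as a definition, but it is not. The SAP cut-off speaks of the last administration, and a drug-free week contains none. Protocol 9.8 has the CRF capture the date of last dose, and SAP 4.5.1 measures exposure to the last recorded dose date. A programmer would naturally use that date and stop at day 30.

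Other points for the plan stand and limit the finding:

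- **Listings.** Protocol 11.2 keeps all reported events in the listings, including late ones. SAP 4.5.2 lists all events, treatment-emergent or not, and 4.5.3 lists deaths, serious events and events leading to withdrawal. A reader might infer that events in the disputed week disappear. If reported, they are lost only from the incidence tables.
- **The SAP as the source.** A reader might infer that the SAP departs from the protocol, or that three windows exist. There are two closing days, and the SAP cut-off matches the second paragraph of 11.2. The contradiction is already inside that section.
- **Withdrawal effects.** A reader might infer that the disputed week is when withdrawal events would appear. Protocol 7.6.1 gives a half-life of about 8 hours, so five half-lives are 5 × 8 = 40 hours; days 31 to 37 come roughly four weeks after that. The drug-free week itself ends in a full final visit, and SAP 4.5.2 does not count worsening seizure frequency as an adverse event. Delayed events remain possible, but nothing in the documents points to this particular week.

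**Conclusion.** The equation of the last dose with the end of taper-off is wrong on the protocol's own schedule and should be corrected. Its size is a 7-day difference in the closing day, affecting onsets on days 31 to 37 after the last dose. The consequences are a treatment-emergent count that depends on the sentence followed, and possibly inconsistent collection between sites.

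The 7 days rest on Protocol 10.16, which is written for early discontinuers on three daily doses. A reader might infer that the gap applies to everyone who stops. The documents do not support that: 9.7.1 allows twice-daily and unequal regimens for which the dose-dropping steps are not defined, no weekly steps are given for the taper at study end, and Section 13 requires an immediate stop after a life-threatening serious event.

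The number of events affected is unknown. A reader might take the 41 of 222 patients (18%) in the predecessor extension who had stopped by 6 months (Protocol 7.4) as a measure of impact. That is all-cause discontinuation in another study and says nothing about events in the disputed week.

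Reliance on spontaneous reports after the final visit is a separate matter. A reader might infer a demonstrated undercount, but the documents give no estimate. They also require known events to be followed to resolution or stabilisation (12.4.1) and every effort at safety follow-up (10.20.2). These provisions do not schedule an enquiry about new events, so ascertainment is passive, but the definitional finding does not depend on it.

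**What to change.** Delete the bracketed equation in Protocol 11.2, 12.4.1, the Appendix A footnote and SAP 4.5.2. Define one adverse-event closing date and use it identically for collection, the treatment-emergent definition and the SAP cut-off. Suggested rule: *30 days after the end of the patient's taper period or, where there was no taper, 30 days after the date of last dose on the CRF.* Replace the second-paragraph definition in 11.2 with a reference to that date.

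The documents do not settle which anchor was intended. Keeping the end of taper preserves the protocol's analysis sentence and study design and loses no events. Do not write 37 days into the text, since the gap is not the same for every regimen or way of stopping.

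The taper passages themselves (9.7.1, 10.16, 10.20.2 and Section 13) need only be reconciled, so that the end of taper is identifiable for every patient; no taper rule is proposed here.

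Cost: wording in both documents, a taper-end date on the CRF if it is not already captured (9.8 names only first- and last-dose dates), and slightly more treatment-emergent events counted.

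Optional and separate: one telephone enquiry about adverse events when the window closes would improve ascertainment, at one call per patient.
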